CFR	Code of Federal Regulations
CRF	Case Report Form
FDA	Food and Drug Administration
GCP	Good Clinical Practice
HIPAA	Health Insurance Portability and Accountability Act
ICF	Informed Consent Form
ICH	International Conference on Harmonization
ICMJE	International Committee of Medical Journal Editors
IND	Investigational New Drug Application
IRB	Institutional Review Board
MedDRA®	Medical Dictionary for Regulatory Activities
MOP	Manual of Procedures
NDA	New Drug Application
OHRP	Office for Human Research Protections
PCP	Primary Care Physician
PHI	Protected Health Information
PI	Principal Investigator
10% PVPI	10% Povidone/1.0% Iodine
SAE	Serious Adverse Event
S-ECC	Severe Early Childhood Caries
SOP	Standard Operating Procedure
WIRB	Western Institutional Review Board

PROTOCOL SUMMARY

Title	Phase 2 Efficacy Evaluation of Advantage Anti-Caries Varnish Acronym Title: Kouruhr Masamwahu
Précis	The purpose of the study is to determine the efficacy of Advantage Anti-Caries Varnish
Objectives	Primary ➤ To determine if Advantage Anti-Caries Varnish (test varnish) is superior to a control varnish containing only fluoride in the prevention of new caries lesions. Secondary ➤ To establish that the response of child participants to the test varnish was not inferior to the control varnish
Study Population	Children 60 to 84 months at time of entry
Phase	2
Number of Sites	One, Pohnpei State, Federated States of Micronesia
Study Duration	27 months (includes 3-month enrollment period followed by 24 months of follow up)
Subject Participation Duration	The total duration of subject participation is 24 months.
Description of Agent or Intervention	Single-center, double-blind, controlled Phase 2 study with parallel groups of children. Subjects will be stratified by EEC/school and then randomized to receive either test varnish or control varnish topically to the teeth. Treatment will be administered quarterly for up to 24 months.
Estimated Time to Complete Enrollment	3 months
Number of Subjects	Total number of subjects planned is: up to 600
Inclusion Criteria	1. The subject's parent or legal guardian must provide signed and dated informed consent (parent permission form). 2. The subject's parent or legal guardian of the subject must be willing and able to comply with study requirements. 3. The subject is aged 60-84 months at the time of the screening visit. 4. The subject must be in good general health as evidenced by medical history.
Exclusion Criteria	1. Known allergy to iodine 2. Known allergy to seafood 3. Known hypersensitivity to fluoride varnish 4. Diagnosis of thyroid disease 5. Chronic, prophylactic use of antibiotics

	6. Treatment with another investigational drug or other intervention within 30 days preceding the Baseline Visit.
Route and Dosage Form	Treatment applied to teeth topically (0.2 mL or control)
Primary Outcome Measures	Efficacy: Surface-level primary molar caries increment (d ₂ mfs) at 24- months post baseline
Secondary Outcome Measures	1. Safety: a. Adverse event occurrence 2. Child response (Facial Image Scale 1-5)
	The proposed sample size of 600 subjects will provide >90% power to demonstrate a 30% or greater reduction in caries in the test group as compared to the control varnish group.

Schematic of Study Design:

1. Key Roles

Individuals:	
Principal Investigator:	[name] Department of Oral Health Sciences University of Washington, Seattle Email: [contact]
Sponsor/Investigator:	[name] Professor of Oral Health Sciences University of Washington, Seattle Email: [contact]
Medical Monitor	[name] Pohnpei State Hospital Pohnpei, FSM
Regulatory Monitor:	[name] [name] Consulting, Inc. [name]
Site Director	[name], BDS Chief of Dental Division Pohnpei State Department of Health Services Pohnpei, FSM
Institution and Locations:	Pohnpei State Department of Health Services Pohnpei, FSM
Biostatistician	[name] Research Associate Professor of Oral Health Sciences University of Washington Seattle, WA Email: [contact]
Coordination Center	Regional Clinical Dental Research Center & Research Coordination Center Institute of Translational Health Sciences [name] [contact] / [contact]

2. Introduction: Background Information and Scientific Rationale

2.1 Background Information

Background: Topical fluorides have been the mainstay in the prevention of dental caries for decades. There is abundant data on sodium fluoride's (NaF) ability to foster remineralization of tooth enamel (Gao et al., 2016). Dental NaF varnish preparations are the recommended vehicle for delivering topical NaF for dental caries prevention and arrest in young children under 6 years of age according to guidelines from the American Dental Association (ADA), the American Academy of Pediatric Dentistry and the US Preventive Services Task Force (Weyant et al., 2013; American Academy of Pediatric Dentistry, 2013; Moyer VA 2014). In children, less than 6 years of age, at high risk for dental caries, the recommendation is application of NaF varnish every three months (Weyant et al., 2013). Fluoride varnishes have been shown to be safe in very young children (Milgrom et al., 2014).

However, topical fluoride alone is not enough to thwart tooth decay in high-risk populations. Caries researchers for some time have suggested strategies that combine an antiseptic with topical fluoride to reduce or eliminate the oral cariogenic bacteria reservoir in addition to topical fluoride which primarily remineralizes enamel (Milgrom et al 2009). Povidone iodine is an FDA-approved and widely used bactericidal antiseptic. For the oral flora, iodine has preferential activities against streptococcal species, pathogens implicated in the causation of dental caries (Tam et al., 2006; Furiga et al., 2008). Moreover, iodine's effectiveness may last as long as 6 months (Caufield et al., 1979).

Studies have examined the chemotherapeutic suppression of oral *Streptococcus mutans* (Sm) by povidone iodine (10%) in children with Severe Early Childhood Caries (S-ECC). In one study, the teeth of children two to six years of age were treated topically with povidone iodine (10%) or saline following dental treatment under general anesthesia for S-ECC (Zhan et al, 2006). Levels of Sm were significantly reduced up to three months in the povidone iodine group. A second study demonstrated suppression of Sm up to 90 days in children with S-ECC who received a single application of povidone iodine (10%) followed by a topical application of 1.23% acidulated phosphate fluoride foam after surgical elimination of active caries lesions (Berkowitz et al 2009).

Other studies have assessed the effect of povidone iodine (10%) on dental caries. A clinical study involving babies in Puerto Rico who were at high risk for S-ECC as they were all colonized by Sm and had decay-promoting feeding behaviors, demonstrated that povidone iodine (10%) applied bimonthly was successful in preventing the development of early tooth decay lesions in the maxillary primary incisors (Lopez et al., 2002). In a randomized clinical trial, povidone iodine (10%) applied bi-monthly significantly reduced the rate of recurrent dental decay at six months following treatment of children under general anesthesia for S-ECC (Amin et al., 2004).

Two cohort studies have tested the effect of combining these two anti-caries agents by sequentially applying povidone iodine (10%) followed 5% NaF varnish. The first study assessed the effect of protecting erupting 1st permanent molars from developing dental caries in children five to six years old ([name] & Milgrom, 2010). The second studied the effect in the primary dentition of children 12 to 30 months (Milgrom, [name] & Mancl, 2011). They demonstrated that treatment with povidone iodine reduced the rate of new decay significantly over the standard of care alone. Yet, to date, such combination products have not been brought to the market. Advantage Anti-Caries Varnish was developed to combine the antiseptic povidone iodine and sodium fluoride varnish into a single product for ease of application, particularly in high caries risk, pre-school age children.

A phase 1 study of the safety of the new varnish was conducted in 12 healthy children with an average age of 47.6 months (WIRB PRO NUM: 20160539). No child evidenced any intra oral erythema or secondary changes as a consequence of the varnish application either immediately or within 24-48 hours post application. Neither were there any adverse effects. The FDA has reviewed the previous safety work and this protocol and issued IND 128835 for this work. The basic dental varnish formula was previously cleared by the FDA as a medical device and is currently on the market. To our knowledge there have been no adverse event reports on this varnish and it has never been withdrawn from the market. Povidone iodine is widely used in children in medicine. It has been used for intraoral application for many years without problems. Dental NaF varnish and povidone iodine have been applied sequentially at the same patient visit by clinicians for some time and two cohort studies have been published with no reports of harms.

2.2 Potential Risks and Benefits

2.2.1 Potential Risks

None of the proposed methods pose any serious risks to the study subjects.

The FDA approves the topical use of 10% PVPI to the skin of children.

Risks from povidone iodine include rash and swelling at the site of application. Iodine can cause thyroid gland problems, but this is rare and is very unlikely at the amount used in this study.

2.2.2 Known Potential Benefits

There are direct benefits to the human subjects participating in this proposal. These include the early detection of caries, its timely management and the possibility of its prevention. All subjects will also receive standard-of-care treatment.

3. Objectives

3.1 Study Objectives

Primary Objective:

To determine if Advantage Anti-Caries Varnish (test varnish) is superior to a control varnish containing only fluoride in the prevention of new caries lesions.

Secondary objectives:

- a) To establish that the response of child participants to the test varnish was not inferior to the control varnish
- b) To document the safety of the test varnish.

3.2 Study Outcome Measures

3.2.1 Primary Outcome Measure

Surface-level primary molar caries increment (d₂mfs) at 24 months post baseline

3.2.2 Secondary Outcome Measures

- Adverse event occurrence
- Facial Image Scale score (1-5)

4. Study Design

This is a single center randomized, double-blind, placebo-controlled, parallel-group trial.

4.1 Rationale for Study Design

The hypothesis is that the test varnish will be superior to the control varnish and will not be inferior in patient response than the control varnish. There will be no difference in the frequency of adverse events.

4.2 Rationale for Dosage

The treatment group will be exposed at baseline and once every three to four months after baseline for a maximum period of 24 months. The control group will be exposed to the control varnish in the same manner. The decision for dosing every three to four months with the test varnish was based on earlier work (Berkowitz, Koo et al. 2009) and the AAPD Standard of Care for children at high risk for dental caries.

5. Study Enrollment and Withdrawal

5.1 Subject Numbers

Up to 600 subjects will be enrolled. Half will be randomized to each arm. If a family has more than one eligible child, each will be allowed to enroll.

In order to be eligible to participate in this study, a subject must meet all of the following criteria:

5.2 Subject Inclusion Criteria

1. The subject's parent or legal guardian must provide signed and dated informed consent (parent permission form).
2. The subject's parent or legal guardian of the subject must be willing and able to comply with study requirements.
3. The subject is aged 48-84 months at the time of enrollment.
4. The subject must be in good general health as evidenced by parent report.

5.3 Subject Exclusion Criteria

A subject who meets any of the following criteria will be excluded from participation in this study:

1. Known allergy to iodine
2. Known allergy to seafood
3. Known hypersensitivity to fluoride varnish
4. Diagnosis of thyroid disease
5. Chronic, prophylactic use of antibiotics
6. Treatment with another investigational drug or other intervention within 30 days preceding the Baseline Visit.

In the event of unique circumstances permitting waiver of any of the above eligibility criteria, documentation of such a waiver must be generated by the Principal Investigator prior to randomization into the study. Enrollment of an otherwise ineligible subject into the study without prior approval of a waiver will be considered a protocol violation.

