6.1.2 Formulation, Packaging, and Labeling

Advantage Anti-Caries Varnish. The active ingredients are 10% (w/v) Povidone Iodine CAS RN 25655-41-8 and 5% (w/v) Sodium Fluoride CAS RN 7681-49-4 in Ethanol 200 Proof. The formulation of the dosage form includes 10% Nt-2 Premium Shellac, 1% sodium phosphate, dibasic anhydrous, 0.5% ammonium phosphate, monobasic, and 1% caramel cream flavor (Bell 29.26303) as inactive ingredients. One and two-year shelf life of the varnish has been established according to Guidance for Industry Q1A(R2) Stability Testing of New Drug Substances and Products (Revision 2, November 2003).

The active control varnish will be the same fluoride varnish without iodine with an appropriate FDA approved food dye added to match the color of the test agent. There will be no difference in the treatment and control varnishes except for the povidone iodine.

The varnishes will be packaged in 12 mL multi use bottles with the following labeling.

Advantage Anti Cavity Varnish or Control Varnish

- Apply as per protocol
- For Investigational Use Only
- Drug Code A or B
- Contact: [name], [contact] (24 hours)

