7.4 Follow-Up Contacts

The subject's teacher will be contacted 48 hours following treatment. If the child is not attending or the teacher knows of a problem, the parent will be contacted to determine if there is a reportable AE. The medical monitor will assign causality. No treatments will be done on Fridays to avoid having to make home visits in order to obtain the basic AE information on the weekend.

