8.3.1. General Health (Medical History and Physical Examination)

The subject's general health status at enrollment will be assessed by medical history using the parent or legal guardian as the informant.

The Study Site Coordinator will rule out a history of thyroid disease and iodine allergy (e.g., allergy to seafood).

All concomitant medications taken by the subject will be recorded at the time of consent and updated at each follow-up study visit (including all prescription and over-the-counter medications, vitamins, and nutritional supplements taken within the past three months).

9. Assessment of Safety

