9.6 Reporting Procedures

9.6.1 Reportable Events

The following incidents will be considered reportable events and will be reported to the Principal Investigator within 24 hours of the site's awareness of the event.

- Serious Adverse Event
- Emergency Treatment Disclosure
- Post-Treatment Adverse Events*, including
 - Nausea
 - Not eating
 - Vomiting
 - Difficulty swallowing or breathing
 - Swelling around the lips or skin on the face
 - Itchiness around the lips or skin of the face
 - Hives or rash

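### Section 5.3 lets any exclusion be waived, including known allergy to the varnish's own ingredients, and does not name who approves the waiver

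*Combined protocol and SAP*

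**What the plan says.** Section 5.3 of the protocol lists six exclusions. The first four are known iodine allergy, known seafood allergy, known hypersensitivity to fluoride varnish, and diagnosed thyroid disease. The closing paragraph opens: "In the event of unique circumstances permitting waiver of any of the above eligibility criteria". It asks the Principal Investigator to document the waiver before randomisation. It adds that enrolling an ineligible child "without prior approval of a waiver will be considered a protocol violation". It does not say what counts as a unique circumstance, who gives the approval, or whether any criterion lies outside the clause.

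The exclusions relate directly to the products. Section 6.1.2 says of the test varnish: "The active ingredients are 10% (w/v) Povidone Iodine", with 5% sodium fluoride as the other active ingredient. Of the comparator it says: "The active control varnish will be the same fluoride varnish without iodine".

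On screening, Section 8.3.1 says: "The Study Site Coordinator will rule out a history of thyroid disease and iodine allergy", giving seafood allergy as an example of the latter. It mentions neither waivers nor hypersensitivity to fluoride varnish.

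**The concern.** An exclusion for known allergy to an ingredient protects the child before the first dose. The protocol recognises the hazard: Section 2.2.1 states "Risks from povidone iodine include rash and swelling at the site of application", and the events in Section 9.6.1 that must be reported within 24 hours include "Swelling around the lips or skin on the face", as well as hives and difficulty breathing. A site could follow Section 5.3 exactly and still randomise a child with a known allergy to an ingredient, with no one outside the investigator's own team having agreed.

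The other safeguards act later. They are the contact described in Section 7.4 (the "teacher will be contacted 48 hours following treatment"), the 24-hour reports, and the Medical Monitor's monthly review under Section 9.2. All would cover a waived child, but only after the varnish has been applied. Section 2.1 reports a phase 1 study of the combined varnish in 12 healthy children. Nothing in the documents supports its use in children with these allergies.

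**Working it through.** The plan gives no figure to reproduce. The check is mainly a reading of Section 5.3 against every section that might bar or control a waiver.

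**Does another section close the gap?**

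- *Section 8.3.1 (screening).* It identifies a child with thyroid disease or iodine allergy, but does not say that such a child cannot then be waived in. Fluoride-varnish hypersensitivity is not covered.
- *Section 13.3 (amendments).* Prior written approval and WIRB approval apply to changes to the protocol. A waiver for one child uses a route the protocol already provides, so it does not clearly fall under this rule.
- *Section 14.7 (violations).* Violations go to the WIRB. Under Section 5.3 the violation is enrolment without an approved waiver, so an approved waiver triggers no report here.
- *Section 5.8 (withdrawal).* Failure to meet entry criteria is a reason for which a child may be withdrawn. This is discretionary, and it is worded for failures that arise or come to light later, not for one known and accepted at entry.
- *Section 10.1 (monitoring).* The Regulatory Monitor reviews source documents and could see a documented waiver. That is retrospective and is not approval.
- *Medical Monitor.* The stated roles are causality assessment, monthly adverse event review and consultation on emergency unblinding. Approving waivers is not among them.

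None of these bars a waiver or gives it independent control.

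**What exposure would follow a waiver?** Allocation is 1:1 (Section 5.6.1).

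- Iodine is in the test arm only: chance of exposure = 1/2.
- Fluoride varnish is in both arms: chance of exposure = 1/2 + 1/2 = 1.
- Application is at baseline and every three to four months for at most 24 months (Section 4.2). Counting the first treatment visit (Section 7.2) and visits 2 to 8 (Section 7.3) gives 1 + 7 = 8 scheduled applications, each of at most 0.2 mL (Section 6.2).

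**Would barring waivers strain recruitment?** Section 5.5 counts 597 children in nine centres in 2015. The protocol gives two enrolment figures.

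- Against the 280 in Section 11.2: 597 − 280 = 317 to spare.
- Against the ceiling of 600 in the synopsis and Section 5.1: 597 − 600 = −3, a shortfall of 3.

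Section 5.5 also allows recruitment from other centres.

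**The case against.** The best defence is that the clause is narrow. It applies only in unusual circumstances, needs a document before randomisation, and treats enrolment without approval as a violation. The dose is small and topical, Section 2.1 reports no harms from sequential use of the two agents, and follow-up after each treatment is in place. The clause may never be used. A child whose seafood allergy is judged unrelated to iodine could be a sensible case for a waiver. Section 2.2.1 calls thyroid problems rare and very unlikely at this amount.

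Much of this stands and limits the point. A reader might infer that no safeguard remains before exposure. The documents do not support that: a documented case-by-case review takes the place of automatic exclusion, and the fault is that the approver is unnamed and need not be independent. A reader might also infer that Section 5.3 contradicts Section 8.3.1. It does not, because the screen can be carried out in full and a waiver granted afterwards. Nor can the clause be read as putting parental consent at risk, since Section 13.4 requires consent in its own right.

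The seafood and thyroid arguments make barring those two waivers a precaution rather than a necessity. They do not touch known iodine allergy or fluoride-varnish hypersensitivity, for which the documents give no reason ever to allow a waiver.

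**Conclusion.** The point holds as a weakness in participant protection. Section 5.3 is a stated permissive rule, not a missing detail. As written, it allows a child with known allergy to an active ingredient to be randomised on Principal Investigator documentation and an approval from no one in particular. The case rests chiefly on the iodine and fluoride-varnish exclusions.

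The consequence for each waived child is clear: a 1 in 2 chance of iodine varnish, or certain exposure to fluoride varnish, assuming the child is treated as allocated. The number of such children is not. The documents give no basis for estimating how many waivers would be granted or how likely a reaction would be, so no overall harm can be calculated. A reader might infer a threat to the efficacy comparison. Nothing in the documents supports this, and no effect on bias or power is claimed.

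**What to change.** Delete the waiver paragraph from Section 5.3. If the sponsor wants to keep some flexibility, the minimum is to state that:

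1. known iodine allergy and known fluoride-varnish hypersensitivity cannot be waived, nor, as a precaution, seafood allergy or thyroid disease; and
2. any other exception needs prior written approval from the Sponsor and the WIRB before randomisation.

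This is a cheap improvement: one paragraph of wording, with no change to design or analysis. The downside is that possibly a few children are not enrolled. It should not be defended by pointing only to the 317 spare children, because that margin disappears if the 600 ceiling is the real target. The better argument is that waivers are meant to be exceptional and that other centres can be used.

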5.4 Discussion of Subject Characteristics

The study population is high risk for dental caries because of their poverty status and lack of access to fluoridated water. The subject population will largely consist of children who are 60 to 84 months of age at the time of enrollment. The study site is Pohnpei State, Federated States of Micronesia (FSM). Under US law and the Compact of Free Association between the US and FSM, this site is considered to be part of the US. There are no intrinsic (genetic or physiologic) or extrinsic (cultural or environmental) characteristics of the population that would influence the safety, efficacy, dosage or dose regiment of the drug. Children consume a diet largely of processed foods from the US mainland and the main pathogenic organism in the etiology of tooth decay is has been shown to be *Streptococcus mutans*, as it is among children in the US proper. These children also use toothpastes produced in the US and regulated by FDA. In addition, this trial will be supervised by a regulatory monitor based in the US and familiar with US regulations. The consent documents will be in English.

